### Sensitivity and Supplementary analyses of the primary efficacy 8.1.2 variable(s)

Sensitivity and supplementary analyses of the primary efficacy endpoint will be conducted:

Approach	Analysis Set	ICE/ICE Strategy	Missing Data Strategy
Sensitivity analysis 1	PPS	NA S	Same with primary analysis
Sensitivity analysis 2 MMRM	FAS US	Same with primary analysis	Data after ICE#3 will be setting to missing and leave missing before running MMRM. No other imputatio before MMRM.
Sensitivity 3	FAS	Same with primary analysis	Observed

Page 33 of 89

Supplementary analysis 1	FAS	ICE#1, ICE#2, and ICE#3 from the primary estimand will all be handled by treatment policy strategy in this supplemental analysis.	LOCF
Supplementary analysis 2	FAS	ICE #1: treatment discontinuation (BMD data collected >70 days after last IMP) will be handled by hypothetical strategy. ICE #2: alternative osteoporosis therapy will be handled by hypothetical strategy.	Data after ICEs will be setting to missing and replaced with LOCF
Supplementary analysis 3	FAS	Same with Supplementary analysis 2	Data after ICEs will be setting to missing and replaced with MI- MAR

For sensitivity analysis 2, a mixed effects model with repeated measures model (MMRM) will be fit with the percent change from Baseline at Months 3 and 6 in BMD of the lumbar spine as the dependent variable, and Baseline BMD, machine type at baseline, interaction of Baseline BMD and machine type at baseline, visit (categorical), treatment (categorical), interaction of treatment and visit, region and interaction of treatment and region as the independent variables. The MMRM analysis will include subject as a random effect, treatment, age strata group (stratification factor), region, visit, and treatment-by-visit interaction as fixed effects, with adjustment for baseline BMD value. The variance structure will allow for heteroskedasticity of variance between treatment groups. The FAS will be used for the repeated measurement model. If model cannot be estimated, region will be excluded from MMRM model.

A blinded data review process will be implemented in which the missingness of data, statistical assumptions, eligibility of definition of categorical variables/thresholds will be assessed. If it turns out that the number of randomized subjects without Baseline and/or without BMD measurement at an on-freatment visit is high, then a sensitivity analysis will be pre-specified under blinded conditions using multiple imputation strategies under the "missing at random" assumption. Depending on the amount of missingness, additional sensitivity analyses under "missing not at random" assumptions may be defined. If the need of such analysis is indicated during the blinded data review process, the method of these analyses will be prespecified in the final SAP before unblinding and database lock.

Further sensitivity analyses will be investigated in DEM of certain critical events listed in Section 4.2 which will be monitored throughout the blinded data review process.

Confidential Page 34 of 89

Due to the exploratory nature of these analyses, even though the p-values will be computed for each analysis in an exploratory manner, formal significance testing will not be conducted.

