13.4 Planned efficacy analysis

13.4.1 Analysis of the primary efficacy variable

The comparison of the percent change from baseline in lumbar spine DXA BMD at Month 6 between treatment groups will be evaluated using an analysis of covariance (ANCOVA) model. The ANCOVA model will include treatment group, baseline BMD value, machine type at baseline, and interaction of baseline BMD value and machine type at baseline as independent variables. Summaries of the results will include least squares (LS) means point estimates of the percent change from baseline for each treatment arm. The 2-sided 95% CI and associated p-value will be provided for the difference between the LS means for romosozumab and placebo.

A sensitivity analysis with a repeated measurements model will be fit with the percent change from baseline at Months 3 and 6 in BMD of the lumbar spine as the dependent variable, and baseline BMD, machine type, interaction of baseline BMD and machine type, visit (categorical), treatment (categorical), and interaction of treatment and visit as the independent variables. The variance structure will allow for heteroskedasticity of variance between treatment groups. Due to the sensitivity nature of this analysis, formal significance testing will not be conducted.

A blinded data review process will be implemented in which the missingness of data, statistical assumptions, and eligibility of definition of categorical variables/thresholds will be assessed. If it turns out that the number of randomized subjects without baseline and/or without BMD measurement at an on-treatment visit is high, then a sensitivity analysis under blinded conditions will be executed using multiple imputation strategies under the "missing at random" assumption.

Furthermore, depending on the amount of missingness and on frequencies of treatment discontinuations, additional sensitivity analyses under "missing not at random" assumptions may be defined as well. If such analyses are needed, they will be prespecified in the SAP before unblinding and database lock.

For these BMD analyses, the FAS will be used. The results from the central imaging vendor will be used in the BMD analyses.

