# 2.5 Study design and conduct

This is a Phase 3 multicenter randomized, DBPC study followed by OL Treatment Period in postmenopausal Chinese women with osteoporosis to evaluate the efficacy, safety and tolerability of romosozumab treatment. The study consists of 4 study periods: Screening Period (Day -35 to Day -1), 6-month DBPC period, 6-month OL Treatment Period, and 3-month FU Period. The overall study design including treatment assignments is depicted in the schematic diagram in Figure 1. For each individual subject, the study will last approximately 16 months. A

03 Mar 2023 OP0002

subject's participation in the study may be extended up to 1 year after the final IMP administration if the subject tests positive for neutralizing antibodies to romosozumab at the EOS Visit or ET Visit.

[figure not shown]
In the DBPC Period, after screening, approximately 300 subjects will be randomized, stratified by age (<75 years,  $\ge 75$  years), in a 2:1 ratio to receive either 210 mg romosozumab subcutaneous (sc) treatment every month (OM) (200 subjects) or matched placebo sc OM (100 subjects) in a blinded manner for 6 months to evaluate if romosozumab treatment for 6 months. compared with placebo, is effective in increasing BMD, as assessed by DXA, at the lumbar spine, total hip, and femoral neck. The primary analysis will be performed using the data obtained from the DBPC Period.

Upon completion of the 6-month DBPC Period, subjects will enter the 6-month OL Treatment Period and receive 210mg romosozumab sc QM for 6 months in an open-label fashion. During this period, all subjects will receive active treatment (romosozumab), 12 months exposure for subjects randomised to romosozumab and 6 months exposure for those randomized to placebo.

After completing the OL Treatment period, subjects will be followed up for an additional 3 months (FU Period) and will complete the EOS Visit (Month 15). Subject participation in the study is concluded after the EOS Visit. Subjects who test positive for neutralizing antibodies to romosozumab at the EOS Visit or ET Visit will be asked to return for additional follow-up testing for up to 1 year after final administration of investigational medicinal product (IMP).

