## • Assumptions for BMD of the femoral neck:

Studies 20070337 and 20120156 showed a minimum treatment difference on femoral neck BMD of 3.2 (95% CI: 2.0 to 4.3) when compared with placebo. The combined upper bounds of the SDs for 20070337 and 20120156 were 4.39 for the romosozumab group and 4.10 for the placebo group.

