# • Resulting sample size:

For the sample size calculations, a 2-group Satterthwaite t-test will be assumed (2-sided on a 5% significance level) which allows for unequal SDs and unequal sample size ratios. Taking into account the upper bounds pooled common SDs and the minimum effect size as assumptions (BMD of the femoral neck outlined above), the sample size of 146 subjects for romosozumab and 73 subjects for placebo would preserve at least 90% power for the percent change from baseline in BMD of the lumbar spine, total hip and femoral neck at Month 6.

To give a reasonable chance to show significance, at least 90% power for all 3 anatomical sites, following a hierarchical testing procedure (see Section 4.5) with safety objectives and dropout taken into account, a total sample size of 300 subjects (ie, 200 subjects in the romosozumab group and 100 subjects in the placebo group) seemed appropriate.

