The comparison of the percent change from Baseline in lumbar spine DXA BMD at Month 6 between treatment groups will be evaluated using an analysis of covariance (ANCOVA) model. The ANCOVA model will include treatment group, age strata group (stratification factor), Baseline BMD value, machine type at baseline, region, and interaction of Baseline BMD value and machine type at baseline as independent variables. Summaries for the results will include least squares (LS) means point estimates of the percent change from Baseline for each treatment arm.. Summaries including the LS mean, standard error, 2-sided 95% CI and associated p-values (unadjusted p-value and adjusted p-value) will be provided for the difference between the LS means for romosozumab and placebo.

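### The MMRM sensitivity analysis in SAP 8.1.2 has two inconsistent term lists, a treatment-by-region term the primary model lacks, and no covariance over visits, so a gap from the primary result could not be put down to missing data alone

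*SAP*

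**What the plan says.** **Primary model.** SAP 8.1.1: "The ANCOVA model will include treatment group, age strata group (stratification factor), Baseline BMD value, machine type at baseline, region", plus the baseline-by-machine interaction. There is no treatment-by-region term. SAP 4.1 gives the same covariates as a rule for all model-based analyses where applicable.

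**MMRM, first sentence (SAP 8.1.2, sensitivity analysis 2).** Baseline BMD, machine type, their interaction, visit, treatment, and "interaction of treatment and visit, region and interaction of treatment and region as the independent variables". Age stratum is not listed.

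**MMRM, second sentence.** "The MMRM analysis will include subject as a random effect, treatment, age strata group (stratification factor), region, visit, and treatment-by-visit interaction as fixed effects", adjusted for baseline BMD. Machine type, baseline-by-machine and treatment-by-region are not listed.

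**Variance and fallback.** SAP 8.1.2 lets the variance differ between treatment groups. It names no within-subject covariance structure, no variance by visit and no degrees-of-freedom method. If the model cannot be estimated, region is dropped; the text does not say what happens to the interaction.

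**Protocol.** Section 13.4.1 ends its term list with "interaction of baseline BMD and machine type, visit (categorical), treatment (categorical), and interaction of treatment and visit as the independent variables". It has no region, treatment-by-region or age term and no random subject effect. SAP 3.9, which lists departures from the protocol, does not mention the MMRM.

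**Secondary endpoints.** SAP 8.2.1 sends their MMRM to the terms of Section 8.1.1, an ANCOVA with no visit or treatment-by-visit term.

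**The concern.** The repeated-measures model has a defined job. Protocol 13.6 lists it among the analyses meant to show that the imputation approach is sound. In the SAP 8.1.2 table it keeps the primary handling of intercurrent events and replaces imputation with a likelihood analysis that uses the Month 3 scans. To do that job, it should differ from the primary analysis in missing-data handling and in as little else as possible.

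As drafted, two other things can change with it: how the three regions are weighted in the Month 6 difference, and how the Month 6 variance is estimated. If the MMRM and the primary ANCOVA then disagreed, nobody could say which change was responsible. Two programmers could also fit different models from the same paragraph.

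**Working it through.** **1. Fixed effects side by side**

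| Term | Primary (8.1.1) | Rule (4.1) | MMRM sentence 1 | MMRM sentence 2 | Protocol MMRM |
|---|---|---|---|---|---|
| Baseline BMD | yes | yes | yes | yes | yes |
| Machine type, baseline-by-machine | yes | yes | yes | no | yes |
| Age stratum | yes | yes | no | yes | no |
| Region | yes | yes | yes | yes | no |
| Treatment-by-region | no | no | **yes** | no | no |
| Visit, treatment-by-visit | n/a | n/a | yes | yes | yes |

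Applying 4.1 restores age stratum to the first list and the machine terms to the second. Treatment-by-region is the only fixed-effect difference left.

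**2. The plan's own figures**

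The sizing rests on "a 2-group Satterthwaite t-test will be assumed (2-sided on a 5% significance level") and states that "the sample size of 146 subjects for romosozumab and 73 subjects for placebo would preserve at least 90% power". The limiting site is the femoral neck, with a "minimum treatment difference on femoral neck BMD of 3.2 (95% CI: 2.0 to 4.3"), so the lower bound is 2.0; SDs are 4.39 and 4.10.

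- Femoral neck SE at 146/73 = sqrt(4.39²/146 + 4.10²/73) = 0.602. Power is 91.0%, so the stated figure reproduces.
- Lumbar spine (difference 6.9, SDs 5.26 and 3.34): SE = 0.585 at 146/73, so 6.9/0.585 = 11.8. At 200/100 the SE is 0.500.

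**3. Region weighting**

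The documents give no region shares; those below are assumptions. With equal region weights, the SE relative to a common-effect model is sqrt(K), where K = sum(1/share)/9:

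| Shares | K | SE factor |
|---|---|---|
| 40/40/20 | 1.111 | 1.054 |
| 45/40/15 | 1.265 | 1.125 |
| 45/45/10 | 1.605 | 1.267 |

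This treats Month 6 on its own. The first sentence holds the regional differences constant over visits. With complete data and equal variances at correlation ρ, the factor is then sqrt(K(1+ρ)/2 + (1−ρ)/2). At an assumed ρ of 0.7 the three factors become 1.046, 1.107 and 1.231, so the table gives upper values for these shares.

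The estimate moves only if effects differ by region. With assumed effects of 7.9/6.9/5.9, the share-weighted contrast is 0.45×7.9 + 0.35×6.9 + 0.20×5.9 = 7.15 at shares 45/35/20, and 7.30 at 50/40/10. The equal-weight contrast is 6.90 in both cases. With 6.9 in every region, both weightings give 6.90.

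**4. Covariance**

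A random subject intercept plus one residual variance per arm gives compound symmetry: Months 3 and 6 share a variance. With complete data, the Month 6 SE relative to the unstructured one is sqrt((1 + r²)/2), where r = SD(Month 3)/SD(Month 6), taken as equal in both arms. Coverage is 2Φ(1.96 × ratio) − 1. The documents give no Month 3 SD, so r is an assumption:

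| r | SE ratio | Understated by | 95% CI coverage |
|---|---|---|---|
| 0.7 | 0.863 | 14% | 90.9% |
| 0.8 | 0.906 | 9% | 92.4% |
| 0.9 | 0.951 | 5% | 93.8% |
| 1.0 | 1.000 | 0 | 95% |

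If r exceeded 1, the error would go the other way.

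A simulation (400 trials per setting, 200/100, lumbar spine SDs, assumed correlation 0.7) agreed. With complete data the two structures gave the same point estimate. At r = 0.8, coverage was 91.8% under compound symmetry and 93.8% unstructured. With nominal 10% to 20% of Month 6 values missing depending on Month 3, mean error at r = 0.8 was +0.06 to +0.09 under compound symmetry and about +0.02 unstructured. At a more extreme r of 0.6 it was +0.10 to +0.15 against about +0.02. All are on a true effect of 6.9. Monte Carlo error on these means is about 0.5/sqrt(400) = 0.025.

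**The case against.** The case against is substantial, and most of it stands.

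- **A reader might infer that the two sentences define incompatible models.** They can be read cumulatively, and SAP 4.1 resolves everything except treatment-by-region. They are inconsistent, not irreconcilable.
- **A reader might infer that the SAP forces equal variance at Months 3 and 6.** It does not say so. That is the literal reading of a random subject effect with heterogeneity only between arms, but a visit-specific residual variance is not ruled out.
- **Equal region weighting is not stated either.** The only LS-means code in the SAP, for the multiple-imputation ANCOVA in Appendix 13.4, uses observed margins. Carried over to the MMRM, that option would avoid the equal-weight inflation. SAP 8.1.2 does not carry it over.
- **Missing-data handling is varied elsewhere.** Sensitivity 3 uses observed data under the primary intercurrent-event strategy. It is a useful check, but only the MMRM is specified as a repeated-measures likelihood analysis using Month 3 under that strategy; supplementary 3 also changes the strategy.
- **A reader might infer that SAP 8.2.1 reuses this model for the hip and femoral neck.** It points to 8.1.1, which has no treatment-by-region term. That is a separate cross-reference fault.
- **Inferential weight is low.** SAP 8.1.2 excludes formal significance testing for these analyses.

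What survives is the stated treatment-by-region term without a weighting, and a random subject effect where a by-visit covariance would serve better.

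**Conclusion.** The point holds as a specification fault in an exploratory analysis. The model as written can change region weighting and the Month 6 variance model together with the missing-data handling it is meant to test.

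Under the assumed region shares, equal weighting would raise the SE by about 5% to 27%, or somewhat less once both visits inform the regional differences. It leaves the estimate alone unless effects differ by region. Compound symmetry would understate the Month 6 SE by about 5% to 14% for r between 0.9 and 0.7, with no effect on the point estimate when data are complete and a small one under the missingness simulated. Region shares, regional effects, r, the correlation and the missingness are all assumptions.

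A reader might go further and infer that the primary conclusion is in doubt. The documents do not support that: the primary ANCOVA is separate and, at the planning values, the lumbar spine effect is 11.8 standard errors at 146/73. Even a 27% larger SE leaves 6.9/(0.585 × 1.27) = 9.3.

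**What to change.** Replace the two sentences in SAP 8.1.2 with one model:

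- **Fixed effects:** the primary ANCOVA covariates (baseline BMD, machine type, their interaction, age stratum, region), treatment, visit and treatment-by-visit. Baseline-by-visit is optional.
- **Region:** drop treatment-by-region. SAP 4.4 and 4.6 already explore effects by region.
- **Covariance:** unstructured over Months 3 and 6, estimated separately by arm, in place of the random subject effect. Name the degrees-of-freedom method and a fallback order.
- **Secondary endpoints:** point the MMRM in SAP 8.2.1 to this model instead of Section 8.1.1.
- **Record:** list the differences from the protocol's repeated-measures model in SAP 3.9.

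Arm-specific variance stays, because both documents ask for it, so one declared difference from the primary ANCOVA remains.

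The cost is a rewritten paragraph, a corrected cross-reference and a few more covariance parameters. No data collection or sample size changes.

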# 8.2 Statistical analysis of the secondary efficacy variables

For the secondary efficacy BMD endpoints during the DBPC Period (at total hip and femoral neck at Month 6), will be performed following the same analyses that for the primary endpoints. The main analysis and sensitivity/supplementary analyses of key secondary endpoints will follow same estimands than the primary endpoint except attribute of "Endpoint". COVID-19 related intercurrent event is also added to the estimand of key secondary endpoints and same strategy in each analysis.

- Percent change from baseline in BMD at the total hip at the end of the DBPC (Month 6) as assessed by DXA
- Percent change from baseline in BMD at the femoral neck at the end of the DBPC Period (Month 6) as assessed by DXA
- Percent change from baseline in BMD at the lumbar spine at the end of OL Treatment Period (Month 12) as assessed by DXA in subjects who are continuing with 6 months of romosozumab treatment after initially being randomized to 6 months of romosozumab treatment in the Double-Blind, Placebo-Controlled Period (for a total of 12 months of romosozumab treatment)
- Percent change from baseline in BMD at the total hip at the end of OL Treatment Period (Month 12) as assessed by DXA in subjects who are continuing with 6 months of romosozumab treatment after initially being randomized to 6 months of romosozumab treatment in the Double-Blind, Placebo-Controlled Period (for a total of 12 months of romosozumab treatment)
- Percent change from baseline in BMD at the femoral neck at the end of OL Treatment Period (Month 12) as assessed by DXA in subjects who are continuing with 6 months of romosozumab treatment after initially being randomized to 6 months of romosozumab treatment in the Double-Blind, Placebo-Controlled Period (for a total of 12 months of romosozumab treatment)
  - The derivation rules specified in Section 8.1.1 will be applied for the calculation of the secondary BMD endpoints as well.

# 8.2.1 Secondary efficacy variables - DBPC Period

For the secondary efficacy BMD endpoints during the DBPC Period (at total hip and femoral neck at Month 6), a percent change from Baseline in DXA BMD will employ an ANCOVA model. The ANCOVA model will include the same independent variables and interactions as described in Section 8.1.1. The FAS will be used for this analysis. This analysis will be performed with adjustment for multiplicity as described in Section 4.5. Nominal (unadjusted) p-values will be provided as well for exploratory purposes.

A sensitivity analysis will be performed on the analysis of the secondary efficacy variable as described in the above paragraph based the PPS. In addition, a MMRM will be fit with the percent change from Baseline at Months 3 and 6 in BMD of the total hip and femoral neck with

the same independent variables and interactions as described in Section 8.1.1. The FAS will be used for these analyses.

For the secondary efficacy BMD endpoints at total hip and femoral neck, the following 2 further sensitivity analyses will be conducted:

Only those values are included in analysis, which were assessed during the period when subjects received IMP and does not apply to any alternative osteoporosis therapy (licensed drugs only). In particular, all values which were assessed more than 70 days after last dose of IMP or were assessed after the first intake of alternative osteoporosis therapy (licensed drugs only) will be considered as missing data and will not be imputed. For one analysis, missing data imputation via LOCF will be applied, and for the other analysis via multiple imputation according to missing at random assumption will be applied.

# 8.2.2 Secondary efficacy variables - OL Treatment Period

For the OL Treatment Period, only the post Month 6 value will be used for imputation, the values in the DBPC Period will not be carried forward into the OL Treatment Period.

For the OL Treatment Period analyses, the secondary efficacy variables are the percent change from Baseline in BMD at lumbar spine, total hip, and femoral neck at the end of OL Period (at 12 months) as assessed by DXA in subjects initially randomized to romosozumab only. The descriptive statistics will be performed for 12 months analysis.

